8.4.2.6. Central Nervous System Vascular Disorders

The Central nervous system vascular disorders search definition is based on the MedDRA version 27.0 Narrow and Broad Terms from the Haemorrhagic central nervous system vascular conditions SMQ, Ischaemic central nervous system vascular conditions SMQ, and Central nervous system vascular disorders, not specified as haemorrhagic or ischaemic SMQ. The PTs are shown below, with Narrow search terms indicated:

Amaurosis fugax ¹	Cerebrovascular disorder ¹
Amyloid related imaging abnormalities	Cerebrovascular insufficiency ¹
Amyloid related imaging abnormality-microhaemorrhages and haemosiderin deposits	Cerebrovascular stenosis ¹
Amyloid related imaging abnormality-oedema/effusion	Chronic cerebrospinal venous insufficiency ¹
Basal ganglia haematoma ¹	Claude's syndrome ¹
Basal ganglia haemorrhage ¹	Congenital cerebrovascular anomaly
Basal ganglia infarction ¹	Cortical hand stroke ¹
Basal ganglia stroke ¹	Delayed ischaemic neurological deficit ¹
Basilar artery occlusion ¹	Dural arteriovenous fistula ¹
Basilar artery perforation ¹	Embolic cerebellar infarction ¹
Basilar artery stenosis ¹	Embolic cerebral infarction ¹
Basilar artery thrombosis ¹	Embolic stroke ¹
Benedikt's syndrome ¹	Epidural haemorrhage ¹
Blood brain barrier defect	Extra-axial haemorrhage ¹
Brachiocephalic arteriosclerosis ¹	Extradural haematoma ¹
Brachiocephalic artery occlusion ¹	Extradural haematoma evacuation ¹
Brachiocephalic artery stenosis ¹	Extraschaemic cerebral haematoma ¹
Brain hypoxia ¹	Foetal cerebrovascular disorder ¹
Brain stem embolism ¹	Foville syndrome ¹
	Haemorrhage intracranial ¹

Brain stem haematoma ¹	Haemorrhagic cerebellar infarction ¹
Brain stem haemorrhage ¹	Haemorrhagic cerebral infarction ¹
Brain stem infarction ¹	Haemorrhagic stroke ¹
Brain stem ischaemia ¹	Haemorrhagic transformation stroke ¹
Brain stem microhaemorrhage ¹	Hypertensive cerebrovascular disease
Brain stem stroke ¹	Hypoxic-ischaemic encephalopathy ¹
Brain stem thrombosis ¹	Inner ear infarction ¹
Brain stent insertion ¹	Internal capsule infarction ¹
CADASIL ¹	Intracerebral haematoma evacuation ¹
	Intracranial haematoma ¹
Capsular warning syndrome ¹	Intracranial haemorrhage neonatal ¹
CARASIL syndrome ¹	Intracranial tumour haemorrhage ¹
Carotid aneurysm rupture ¹	Intraventricular haemorrhage ¹
Carotid angioplasty ¹	Intraventricular haemorrhage neonatal ¹
Carotid arterial embolus ¹	Ischaemic cerebral infarction ¹
Carotid arteriosclerosis ¹	Ischaemic stroke ¹
Carotid artery bypass ¹	Jugular vein embolism ¹
Carotid artery disease ¹	Lacunar infarction ¹
Carotid artery dolichoectasia	Lacunar stroke ¹
Carotid artery insufficiency ¹	Lateral medullary syndrome ¹
Carotid artery occlusion ¹	Medullary compression syndrome
Carotid artery perforation ¹	Meningorrhagia ¹
Carotid artery restenosis ¹	Middle cerebral artery stroke ¹
Carotid artery stenosis ¹	Migrainous infarction ¹
Carotid artery stent insertion ¹	Millard-Gubler syndrome ¹
	Moyamoya disease ¹
	Occipital lobe stroke ¹
	Parietal lobe stroke ¹
	Perinatal stroke ¹
	Periventricular haemorrhage neonatal ¹
	Pituitary apoplexy ¹

Carotid artery stent removal ¹	Pituitary haemorrhage ¹
Carotid artery thrombosis ¹	Post cardiac arrest syndrome ¹
Carotid endarterectomy ¹	Post procedural stroke ¹
Carotid revascularisation ¹	Precerebral arteriosclerosis ¹
Central nervous system haemorrhage ¹	Precerebral artery embolism ¹
Central nervous system vasculitis ¹	Precerebral artery occlusion ¹
Cerebellar artery occlusion ¹	Precerebral artery thrombosis ¹
Cerebellar artery thrombosis ¹	Primary familial brain calcification
Cerebellar atherosclerosis ¹	Pseudo-occlusion of internal carotid artery ¹
Cerebellar embolism ¹	Putamen haemorrhage ¹
Cerebellar haematoma ¹	Retinal artery occlusion ¹
Cerebellar haemorrhage ¹	Reversible cerebral vasoconstriction syndrome ¹
Cerebellar infarction ¹	Reversible ischaemic neurological deficit ¹
Cerebellar ischaemia ¹	Ruptured cerebral aneurysm ¹
Cerebellar microhaemorrhage ¹	Sigmoid sinus thrombosis ¹
Cerebellar stroke ¹	Sneddon's syndrome
Cerebral amyloid angiopathy	Spinal artery embolism ¹
Cerebral aneurysm perforation ¹	Spinal artery thrombosis ¹
Cerebral aneurysm ruptured syphilitic ¹	Spinal cord haematoma ¹
Cerebral angioplasty ¹	Spinal cord haemorrhage ¹
Cerebral arteriosclerosis ¹	Spinal cord hypoxia ¹
Cerebral arteriovenous malformation haemorrhagic ¹	Spinal cord infarction ¹
Cerebral arteritis ¹	Spinal cord ischaemia ¹
Cerebral artery embolism ¹	Spinal epidural haematoma ¹
Cerebral artery occlusion ¹	Spinal epidural haemorrhage ¹
Cerebral artery perforation ¹	Spinal stroke ¹
Cerebral artery restenosis ¹	Spinal subarachnoid haemorrhage ¹
Cerebral artery stenosis ¹	Spinal subdural haematoma ¹
Cerebral artery stent insertion ¹	Spinal subdural haemorrhage ¹
Cerebral artery thrombosis ¹	Spinal vascular disorder
Cerebral bypass surgery ¹	Spinal vessel congenital anomaly
	Stroke in evolution ¹
	Subarachnoid haematoma ¹

Cerebral capillary telangiectasia ¹	Subarachnoid haemorrhage ¹
Cerebral circulatory failure ¹	Subarachnoid haemorrhage neonatal ¹
Cerebral congestion ¹	Subclavian steal syndrome ¹
Cerebral cyst haemorrhage ¹	Subcortical stroke ¹
Cerebral gas embolism ¹	Subdural haematoma ¹
Cerebral haematoma ¹	Subdural haematoma evacuation ¹
Cerebral haemorrhage ¹	Subdural haemorrhage ¹
Cerebral haemorrhage foetal ¹	Subdural haemorrhage neonatal ¹
Cerebral haemorrhage neonatal ¹	Superior sagittal sinus thrombosis ¹
Cerebral hypoperfusion ¹	Susac's syndrome
Cerebral infarction ¹	Temporal artery stenosis ¹
Cerebral infarction foetal ¹	Thalamic infarction ¹
Cerebral ischaemia ¹	Thalamic stroke ¹
Cerebral microangiopathy	Thalamus haemorrhage ¹
Cerebral microembolism ¹	Thrombotic cerebral infarction ¹
Cerebral microhaemorrhage ¹	Thrombotic stroke ¹
Cerebral microinfarction ¹	Transient ischaemic attack ¹
Cerebral revascularisation ¹	Transverse sinus thrombosis ¹
Cerebral septic infarct ¹	Vascular encephalopathy ¹
Cerebral small vessel ischaemic disease ¹	Vascular stent occlusion ¹
Cerebral thrombosis ¹	Vascular stent stenosis ¹
Cerebral vascular occlusion ¹	Vertebral artery arteriosclerosis ¹
Cerebral vasoconstriction ¹	Vertebral artery occlusion ¹
Cerebral venous sinus thrombosis ¹	Vertebral artery perforation ¹
Cerebral venous thrombosis ¹	Vertebral artery stenosis ¹
Cerebrovascular accident ¹	Vertebral artery thrombosis ¹
Cerebrovascular arteriovenous malformation	Vertebrobasilar dolichoectasia

¹Narrow term.

8.4.2.7. Embolic and Thrombotic Events

The Embolic and thrombotic events search definition is based on the MedDRA version 27.0

Embotic and thrombotic events, venous SMQ. The PTs are listed below, and all will be

considered Narrow search terms:

Aseptic cavernous sinus thrombosis	Pulmonary embolism
Axillary vein thrombosis	Pulmonary infarction
Brachiocephalic vein occlusion	Pulmonary microemboli
	Pulmonary oil microembolism
Brachiocephalic vein thrombosis	Pulmonary thrombosis
Budd-Chiari syndrome	Pulmonary vein occlusion
Catheterisation venous	Pulmonary veno-occlusive disease
Cavernous sinus thrombosis	Pulmonary venous thrombosis
Central venous catheterisation	Renal vein embolism
Cerebral venous sinus thrombosis	Renal vein occlusion
Cerebral venous thrombosis	Renal vein thrombosis
Compression garment application	Retinal vein occlusion
Deep vein thrombosis	Retinal vein thrombosis
Deep vein thrombosis postoperative	Septic pulmonary embolism
Embolism venous	SI QIII TIII pattern
	Sigmoid sinus thrombosis
Hepatic vein embolism	Spermatic vein thrombosis
Hepatic vein occlusion	Splenic vein occlusion
	Splenic vein thrombosis
Hepatic vein thrombosis	Subclavian vein embolism
Homans' sign positive	Subclavian vein occlusion
Iliac vein occlusion	Subclavian vein thrombosis
Inferior vena cava syndrome	Superior sagittal sinus thrombosis
Inferior vena caval occlusion	Superior vena cava occlusion
Jugular vein embolism	Superior vena cava syndrome
Jugular vein occlusion	Thrombophlebitis
Jugular vein thrombosis	Thrombophlebitis migrans
Mahler sign	Thrombophlebitis neonatal
May-Thurner syndrome	Thrombosed varicose vein
Mesenteric vein embolism	
Mesenteric vein thrombosis	Thrombosis corpora cavernosa
Mesenteric venous occlusion	Transverse sinus thrombosis
	Vascular graft
Obstetrical pulmonary embolism	Vena cava embolism
Obstructive shock	Vena cava filter insertion
Ophthalmic vein thrombosis	Vena cava filter removal
Ovarian vein thrombosis	Vena cava thrombosis

Paget-Schroetter syndrome	Venogram abnormal
Pelvic venous thrombosis	Venoocclusive disease
Penile vein thrombosis	Venoocclusive liver disease
Peripheral vein occlusion	Venous angioplasty
Peripheral vein thrombosis	
Peripheral vein thrombus extension	Venous occlusion
Phlebectomy	Venous operation
Portal vein cavernous transformation	Venous recanalisation
Portal vein embolism	Venous repair
Portal vein occlusion	Venous stent insertion
Portal vein thrombosis	Venous thrombosis
Portosplenomesenteric venous thrombosis	Venous thrombosis in pregnancy
Post procedural pulmonary embolism	Venous thrombosis limb
Post thrombotic syndrome	Venous thrombosis neonatal
Postoperative thrombosis	Visceral venous thrombosis
Postpartum venous thrombosis	

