### **Medical Conditions**

1. Participant has any of the following:
  - Signs of bowel obstruction who require parenteral nutrition.
  - Malabsorption syndrome or preexisting gastrointestinal conditions that may impair absorption of nirogacestat (e.g., gastric bypass, lap band, or other gastric procedures that would alter absorption).
2. Participant has experienced any of the following within 6 months of signing informed consent:
  - Clinically significant cardiac disease (New York Heart Association Class III or IV);
  - Myocardial infarction;
  - Severe/unstable angina;
  - Coronary/peripheral artery bypass graft;

- Symptomatic congestive heart failure;
- Cerebrovascular accident;
- Transient ischemic attack; or
- Symptomatic pulmonary embolism.

3. Participant has abnormal QT interval corrected by Fridericia's formula (> 470 msec for female participants, or > 480 msec for participants with bundle branch block) after electrolytes have been corrected at Screening.
4. Participant has congenital or acquired long QT syndrome or a history of additional risk factors for Torsades de Pointes (TdP) (e.g., heart failure, hypokalemia, family history of Long QT Syndrome).
5. Participant has current or chronic history of liver disease or known hepatic or biliary abnormalities (except for Gilbert's syndrome or asymptomatic gallstones).
6. Participant has had a major surgical procedure, open biopsy, or significant traumatic injury within 28 days prior to the first dose of study treatment.
7. Participant has a history of other invasive malignancies, with the exception of non-melanoma skin cancer, are excluded if there is any evidence of other malignancy being present within the last 5 years. Participants are also excluded if their previous cancer treatment contraindicates this protocol therapy.
8. Participant has CTCAE v5.0 Grade > 1 toxicity from prior therapy (except alopecia, anorexia or CTCAE grade 2 peripheral neuropathy).
9. Palliative radiotherapy with a limited field of radiation within 14 days or with wide field of radiation or to more than 30% of bone marrow within 28 days prior to the first dose of study treatment.

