5.6.3. Safety Topics of Special Interest

Safety topics of special interest have been identified based on review of safety data from prior studies with nirogacestat and include additional AEs beyond those specified in Protocol Section 11.3.1 as adverse events of special interest (AESIs). These safety topics of interest, including AESIs determined by the investigators for this study, will be summarized on separate tables. These safety topics, including AESIs, are defined for analysis purposes in different ways, including by using standardized MedDRA queries (SMQ) or customized MedDRA queries, and whether an investigator determined that an event was an AESI.

Unless specified otherwise, the incidence of AESIs based on the investigator's determination will be summarized by SOC and PT in tables and listed separately in participant data listings, and those by using defined lists of specific MedDRA PTs without regard to the investigator's designation of the reported event as an AESI will be summarized similarly.

For the safety topics of special interest (including AESIs) defined using standardized MedDRA queries (SMQ) or customized MedDRA queries, the specific MedDRA PTs for inclusion are all listed in Appendix 8.4 under the following groups. Safety topics for which narrow and broad terms are identified, only narrow terms are used for summary tables. The safety topics will be summarized by SOC and PT based on the Safety Analysis Set.

- Hypersensitivity
- Skin Disorder and Rash
- Hepatotoxicity
- Electrolyte Disorder
- Non-melanoma Skin Cancer
- Musculoskeletal Disorders
- Bone Fractures
- Mucositis/Stomatitis

- Hematologic Disorders
- Opportunistic Infections
- Central Nervous System Vascular Disorders
- Embolic and Thrombotic Events
- Cardiac Rhythm Disturbances
- Upper Respiratory Tract Infections
- Diarrhea

In addition to the summaries by SOC and PT as described above, separate summaries for concomitant medication use will be presented for the following safety topics:

- Hypophosphataemia (A subset of Electrolyte Disorder terms)
- Upper Respiratory Tract Infection
- Diarrhea
- Skin and Subcutaneous Rash (Broad and Narrow; a subset of Skin Disorder and Rash terms)
- Skin and Subcutaneous Rash (Narrow; a subset of Skin Disorder and Rash terms)

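### The safety topic that SAP 5.6.3 and 8.4.2.7 title as embolic and thrombotic events is defined by venous terms only, so its table under-counts what its title covers

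*SAP*

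**What the plan says.** SAP 5.6.3 sets out 15 query-based safety topics, one of them "Embolic and Thrombotic Events". The appendix heading, "8.4.2.7. Embolic and Thrombotic Events", repeats the name without limit. The definition beneath that heading rests on one source, the "Embotic and thrombotic events, venous SMQ", followed by a list of preferred terms that are all treated as narrow.

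Two rules in SAP 5.6.3 govern what is counted. On content: "the specific MedDRA PTs for inclusion are all listed in Appendix 8.4 under the following groups". On breadth: "Safety topics for which narrow and broad terms are identified, only narrow terms are used for summary tables".

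The neighbouring topic, SAP 8.4.2.6, is built more widely. It joins a haemorrhagic query, the "Ischaemic central nervous system vascular conditions SMQ" and the "Central nervous system vascular disorders, not specified as haemorrhagic or ischaemic SMQ" into one list.

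**The concern.** The topic's name promises all embolic and thrombotic events, while its definition delivers the venous ones. The word that limits the scope appears only in an appendix sentence. Other topic names in SAP 5.6.3 state their own limits: skin cancers are non-melanoma, respiratory infections are upper tract, and vascular disorders are those of the central nervous system.

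A topic query exists to gather related preferred terms that would otherwise be scattered. If an arterial or unspecified-vessel event occurs and the plan is followed exactly, the row with the general name does not move. A reader of that row could then take a venous count for the whole embolic and thrombotic count. The trial has one arm, so there is no comparator column to prompt a second look.

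**Working it through.** The plan gives no figure to reproduce here. The check compares the title, the term list and the other topics.

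1. **Is the list closed?** Yes. SAP 5.6.3 makes the Appendix 8.4 lists the full definition of the query-based topics, so an unlisted term adds 0 to the topic table.

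2. **What is in the 8.4.2.7 list?** It has 99 distinct preferred terms. A search for the stems arter-, aort-, coron-, myocard- and cardiac found none. Exact matches were 0 for each of Myocardial infarction, Acute myocardial infarction, Peripheral artery occlusion, Peripheral arterial occlusive disease, Thrombosis and Embolism. The nearest entries are Embolism venous, Venous thrombosis, Postoperative thrombosis and Thrombosis corpora cavernosa.

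3. **Does another Appendix 8.4 topic supply the missing terms?**
   - *CNS vascular disorders (8.4.2.6)* covers cerebral, carotid, vertebral, spinal and retinal arterial events. It also has a few neighbours marked narrow: Brachiocephalic artery occlusion, Subclavian steal syndrome, Vascular stent occlusion. It has no coronary term and no limb or visceral artery term.
   - *Cardiac rhythm disturbances (8.4.2.8)* has no infarction term. Cardiac arrest is listed but not marked narrow, so it stays out of the summary tables. Sudden cardiac death is narrow, so a death coded that way would be counted there.
   - *Hypersensitivity (8.4.1.1)* has Kounis syndrome, which is not a general infarction term.
   - *Opportunistic infections (8.4.2.5)* has Septic embolus, not marked narrow.
   - *Hepatotoxicity (8.4.1.3)* has Hepatic artery flow decreased and Splenic artery embolisation, neither marked narrow.

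4. **Where would a participant be counted if this were her only event?**

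| Preferred term | Embolic and thrombotic table | Other topic table | General TEAE tables |
|---|---|---|---|
| Deep vein thrombosis | 1 | 0 | yes |
| Cerebral venous sinus thrombosis | 1 | 1 (CNS) | yes |
| Cerebral infarction | 0 | 1 (CNS) | yes |
| Myocardial infarction | 0 | 0 | yes |
| Peripheral artery occlusion | 0 | 0 | yes |
| Thrombosis (vessel not recorded) | 0 | 0 | yes |

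The last three rows are the gap.

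5. **Could avoidance of double counting explain the venous limit?** No. Six terms stand in both 8.4.2.6 and 8.4.2.7: Cerebral venous sinus thrombosis, Cerebral venous thrombosis, Jugular vein embolism, Sigmoid sinus thrombosis, Superior sagittal sinus thrombosis and Transverse sinus thrombosis. The plan already accepts overlap between these topics.

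**The case against.** The strongest reply is that nothing is concealed. SAP 8.4.2.7 says directly under its heading that the query is venous, and it prints every term. The mock-up tables are separate documents (SAP 8.3), so their titles may already say venous. SAP 5.6.3 and 8.4.2 say the additional topics came from safety data of prior nirogacestat studies, and a venous scope may follow from those data. No document requires an arterial topic. Protocol 4.3 names no arterial or thromboembolic risk, and none is among the adverse events of special interest in Protocol Table 9. Exclusion criterion 2, which includes "Coronary/peripheral artery bypass graft" and myocardial infarction, is an eligibility rule. It does not show a drug-related arterial risk.

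All of this stands, and it limits the point to scope and label. It does not remove the mismatch, because both visible SAP sections use the unlimited name and neither gives a reason for a venous limit. If the limit is intended, the name should carry it.

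Three stronger readings are tempting, and the documents do not support them.

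- A reader might infer that arterial events go unreported. SAP 5.6.2 tabulates all TEAEs, serious TEAEs and grade 3 or higher TEAEs by system organ class and preferred term, and lists all adverse events.
- A reader might infer that every arterial event escapes the topic tables. SAP 8.4.2.6 counts those named in step 3 of the working.
- A reader might want a probability of a missed event, or a confidence limit for a zero row. The documents give no arterial risk, and SAP 5.6.2 and 5.6.3 plan counts and percentages for these tables, without intervals. The 53 participants in SAP 5.8 are an enrolment count, not a stated size of the Safety Analysis Set.

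**Conclusion.** The point holds as a mismatch between title and content. Under the plan as written, the embolic and thrombotic table is a venous table. Coronary events such as myocardial infarction, limb and visceral arterial occlusion, and events coded simply as Thrombosis or Embolism count in no safety-topic table. The exceptions are events coded to a specific term listed elsewhere, such as Sudden cardiac death or Kounis syndrome.

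The size is definitional: 0 of 99 listed terms is arterial or coronary. For scale only, if the Safety Analysis Set were the 53 enrolled, each participant with such an event as her only one would leave the row short by 1/53 = 1.9 percentage points. How many there would be cannot be said from the documents.

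The conclusion rests on the printed lists being complete, as SAP 5.6.3 states. It does not depend on the unseen table shells, although a venous title there would already cure part of it. No primary or secondary endpoint, adverse event of special interest or design figure is affected. The change should be made, and it is small.

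**What to change.** In SAP 8.4.2.7, add the arterial and the unspecified or mixed-vessel embolic and thrombotic terms, and report venous, arterial and unspecified sub-rows with an overall row. This layout is a new proposal. SAP 8.4.2.6 is a precedent for joining several queries, but it merges them into one list without sub-rows. Add a footnote that cerebral events may also appear under 8.4.2.6, as the six shared venous terms already do.

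If the venous scope is intended, retitle the topic Venous Embolic and Thrombotic Events in SAP 5.6.3, in SAP 8.4.2.7 and in the table shells.

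Retitling costs only wording. The fuller change costs a longer term list and one re-run of an existing table, with no new data. Its downside is that the overall row may look slightly less favourable and would not match any venous-only tables in other nirogacestat reports. The venous sub-row keeps that comparison.

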8.4.2.8. Cardiac Rhythm Disturbances

The Cardiac rhythm disturbances search definition is based on the MedDRA version 27.0

Narrow and Broad Terms from the Arrhythmia related investigations, signs and symptoms SMQ.

The PTs are shown below, with Narrow search terms indicated:

Chronotropic incompetence ¹	Electrocardiogram ambulatory abnormal
Early repolarisation syndrome ¹	
Electrocardiogram repolarisation abnormality ¹	Electrocardiogram change
Electrocardiogram RR interval abnormal ¹	
Electrocardiogram RR interval prolonged ¹	Heart rate abnormal
Electrocardiogram RR interval shortened ¹	
Electrocardiogram U wave inversion ¹	Heart rate decreased
Electrocardiogram U wave present ¹	Heart rate increased
Electrocardiogram U-wave abnormality ¹	Loss of consciousness
Sudden cardiac death ¹	Palpitations
Bezold-Jarisch reflex	Rebound tachycardia
Bradycardia	Respiratory sinus arrhythmia magnitude abnormal
Cardiac arrest	Respiratory sinus arrhythmia magnitude decreased
Cardiac death	Respiratory sinus arrhythmia magnitude

increased

Cardiac telemetry abnormal	Sudden death
Cardio-respiratory arrest	Syncope
Central bradycardia	Tachycardia
Cerebrocardiac syndrome	
Electrocardiogram abnormal	Tachycardia paroxysmal

¹Narrow term

8.4.2.9. Upper Respiratory Tract Infections

The Upper respiratory tract infections search definition based on the following selected MedDRA version 27.0 PTs:

Acute sinusitis	Sinusitis
Upper respiratory tract infection	Viral upper respiratory tract infection

8.4.2.10. Diarrhea

The Diarrhea search definition is based on the MedDRA version 27.0 PT of Diarrhoea.

Plan Version History

Version	Effective Date	Changes	Author / Modified by
1.0	17-Feb-2023	NA	[name]
2.0	03-Jun-2024	See summary below	[name]
3.0	28-Oct-2024	See summary below	[name]

Change History Summary

Version	Modifications
1.0	Initial Version
2.0	PFS-6 was redefined as a survival probability for consistency with the Kaplan-Meier methodology which was intended to be used to estimate this endpoint.
2.0	Definitions and analysis methods were added for PFS and OS.
2.0	Progression-free survival on continued nirogacestat treatment and PFS2 were added due to protocol amendment.
2.0	Miscellaneous formatting and typographical changes.
2.0	Statement was added for why the planned interim assessment using Bayesian approach as mentioned in the protocol was not performed.
2.0	Analysis of safety topics of special interest identified using standardized MedDRA queries (SMQ) or customized MedDRA queries was added.
3.0	Section 5.6.2 - Added a summary table for serious TEAEs by maximum severity (Grade)
3.0	Section 5.6.6 - Rows for the worst post-baseline change from baseline added to the ECG summary table.
3.0	Section 5.6.7 - Rows for the worst post-baseline change from baseline added to the vital signs summary table.
3.0	Section 8.4.1.4 Electrolyte disorder PTs were revised. Added new electrolyte disorder analyses (summary table and shift table).

Certificate Of Completion

Envelope Id: 40641299A5654F08AF98E3810FA56FF4

Status: Completed

Subject: Complete with DocuSign: NIR-OGT-201 SAP V3.0 28Oct2024.pdf

Source Envelope:

Document Pages: 100

Signatures: 4

Envelope Originator:

Certificate Pages: 5

Initials: 0

[name]

AutoNav: Enabled

[name]

Enveloped Stamping: Disabled

5th Floor

Time Zone: (UTC-05:00) Eastern Time (US & Canada)

[name]

[contact]

IP Address: [name]

Record Tracking

Status: Original

Holder: [name]

Location: DocuSign

29-Oct-2024 | 10:33

[contact]

Signer Events**Signature****Timestamp**

[name]

[name]

Sent: 29-Oct-2024 | 10:37

[contact]

Viewed: 29-Oct-2024 | 10:37

Security Level: Email, Account Authentication
(Required)

Signed: 29-Oct-2024 | 10:38

Signature Adoption: Pre-selected Style

Signature ID:

FC9A7027-5907-4B62-B0EB-8FAC79DE2641

Using IP Address: [name]

With Signing Authentication via DocuSign password

